7.8.3. Exploratory Efficacy Analysis

All other exploratory efficacy endpoints listed in Section 4.1.6 will be analyzed based on Full Analysis Set with confirmed fibrosis stage F2 or F3 and NAS ≥ 4 at baseline per 3-panel consensus read unless otherwise specified. Subject FAST score defined below will also be analyzed.

$$\text{FAST} = \{\exp(-1.65 + 1.07 \times \ln(\text{LSM}) + 2.66 \times 10^{-8} \times \text{CAP}^3 - 63.3 \times \text{AST}^{-1})\} / \{1 + \exp(-1.65 + 1.07 \times \ln(\text{LSM}) + 2.66 \times 10^{-8} \times \text{CAP}^3 - 63.3 \times \text{AST}^{-1})\}$$

For all proportion endpoints, the same stratified CMH methodology as the analysis of primary efficacy endpoints (described in Section 7.8.1) will be used to compare the differences of responder rate in each pegozafermin group versus placebo.

For change from baseline and percent change from baseline endpoints listed Section 4.1.6, descriptive summaries of absolute value and change from baseline at Week 24 will be provided. If there is only a single scheduled post-baseline assessment in Main Study, change from baseline will be analyzed by analysis of variance (ANCOVA) with treatment group, baseline measurement, and two stratification factors as covariates. Otherwise, MMRM method will be used as described in Section 7.8.2. Same as secondary efficacy endpoints, non-parametric van Elteren test stratified by T2DM status (yes vs. no) and fibrosis stage (F2 vs. F3) will be performed if the MMRM (ANCOVA) model assumptions are severely violated. The location shift estimate, and Hodges-Lehmann 2-tailed 95% confidence interval will be presented. For the comparison between each pegozafermin group and placebo, if small cell counts (<5) render the van Elteren test inappropriate, the un-stratified Wilcoxon rank-sum test will be used instead.

7.9. Patient Report Outcome (PRO) Analysis

All PRO summaries will be provided based on the observed data for the Full Analysis Set with confirmed fibrosis stage F2 or F3 and NAS ≥ 4 at baseline per 3-panel consensus read.

Chronic Liver Disease Questionnaire - NAFLD-NASH (CLDQ NAFLD-NASH)

CLDQ NAFLD-NASH contains 36 items (questions) grouped into 6 HRQL domains:

- Abdominal symptoms
- Activity
- Emotional
- Fatigue
- Systemic symptoms
- Worry

Each item's response ranges from 1 to 7. The score of each domain is calculated as the average of the domain's items (sum of all item's response divided by the number of non-missing items). The total CLDQ-NAFLD score will be calculated as an average of the six domain scores.

No imputation will be done for missing value. Surveys with more than 4 missing item responses will be excluded. If there is more than one missing item in one domain, missing value will be assigned for that domain. Total score will be set to missing if any domain score is missing.

CLDQ NAFLD-NASH summary statistics along with the change from baseline will be provided for each domain and total score, based on the full analysis set.

7.9.1. Work Productivity and Activity Impairment Questionnaire for NASH (WPAI-NASH)

WPAI-NASH includes 4 scores on a scale of 0 to 100%: absenteeism (the percentage of work time missed because of one's health), presenteeism (the percentage of impairment experienced while at work because of one's health), overall work impairment (a combination of absenteeism and presenteeism) and activity impairment (the percentage of impairment in daily activities because of one's health).

Summary statistics will be provided for absenteeism, presenteeism, overall work impairment, and activity impairment respectively.

7.9.2. Europe Quality of Life Group 5 Dimension 5 Level Questionnaire (EQ-5D-5L)

The EQ-5D-5L consists EQ-5D descriptive system and the EQ VAS.

EQ-5D descriptive system comprises five dimensions (mobility, self-care, usual activities, pain/discomfort and anxiety/depression). Each dimension has 5 levels (no problems, slight problems, moderate problems, severe problems, and extreme problems) with scale 1 to 5. Each domain will be summarized categorically (1-5).

EQ VAS score ranges from 0 (worst imaginable health) to 100 (best imaginable health). Descriptive summary statistics for the EQ VAS scores and the change from baseline will be provided.

7.9.3. The Appetite Sensations Visual Analog Scale (VAS)

In this study, VAS measures hunger; satiety; fullness; prospective food consumption; and desire to eat something fatty, salty, sweet, or savory, on a scale of 0 to 100.

Summary statistics will be provided for each domain.

7.9.4. Liver-related Pain and Discomfort Questionnaire

Liver-related Pain and Discomfort Questionnaire data will be listed.

7.10. Safety Analysis for Main Study

All safety analyses of Main Study will be performed on the Safety Analysis Set. Safety data presented by treatment group will be summarized on an 'as treated' basis. Safety variables include TEAEs, clinical laboratory parameters, ECG, vital signs, physical examination, bone mass density, and immunogenicity.

7.10.1. Adverse Events

Subject incidence of TEAEs will be tabulated by MedDRA (Version 24.0) system organ class, MedDRA preferred term, and treatment groups. All TEAEs, all treatment-emergent related AEs, all TESAEs, and all treatment-emergent serious related AEs, the most severe Common Terminology Criteria for Adverse Events (CTCAE) grade, TEAEs leading to dose interruption, TEAEs leading to IP discontinuation, and TESAEs leading to IP discontinuation will be summarized. Subjects will be counted only once within a SOC and Preferred Term (PT), even if the subject experienced more than one TEAE within a specific SOC and PT, and PT only.

Selected TEAE analyses will be repeated in subgroups including age, sex, race, and BMI.

All AEs, SAEs, AEs leading to IP interruption or discontinuation, fatal AEs, and COVID-19 related AEs will be listed with TEAE flags included.

Clinical Laboratory Parameters

Clinical laboratory tests listed in ([Clinical Laboratory Tests](#)) will be collected during the study.

For all other assessments that are below the lower limit of quantification will be imputed to half of the lower limit of quantitation (LLOQ) for summarization; assessments that are above the upper limit of quantification will be imputed to the upper limit of quantitation (ULOQ) for summarization. For listings, records that are LLOQ or ULOQ will be listed as such together with the imputed value in separate columns.

For all hematology, biochemistry urinalysis tests, coagulation factors, lipid assessments, and selected other laboratory assessments, descriptive summaries of absolute values and change from baseline at each scheduled assessment will be produced by treatment groups, the number and percentage of subjects with abnormal laboratory values will be summarized.

Shifts (low/normal/high) from the relevant baseline tables based on the normal ranges will be constructed. The shifts will be performed from the baseline to each post-baseline visit, and to minimum and maximum post-baseline visit.

A summary of suspected liver injury cases according to drug induced liver injury (DILI) criteria will also be presented ([Table 6](#)).

Table 6: Suspected liver injury cases according to drug induced liver injury (DILI) criteria

Baseline Value of ALT/AST	Criteria to discontinue investigational product
>ULN and <2× ULN	ALT or AST >5× baseline value
>=2× ULN but <5× ULN	ALT or AST >3× baseline value
>=5× ULN	ALT or AST >2× baseline value
>ULN	ALT or AST >2× baseline value and (BILI >2× ULN or INR >0.2)
Within Normal Range	ALT or AST >8× ULN
	ALT or AST >5× ULN
	ALT or AST >3× ULN and (BILI >2× ULN or INR >1.5)

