7.1.1. Monitoring and Discontinuation for Suspected Drug-induced Liver Injury (DILI)

Liver chemistry will be evaluated as specified in the SoA (Section [1.3](#)).

Per FDA recommendations, the following criteria for elevations in liver transaminases or bilirubin will be used for closely monitoring, discontinuing, or temporarily interrupting IP.

Definition of baseline ALT and AST values

Baseline value is defined as an average of ALT and AST values performed during Screening and the Baseline (Day 1) visit, as follows:

ALT/AST Screening Assessments			Day 1 ALT/AST Assessment	Baseline Value
Assessment 1	Assessment 2	Assessment 3 (if applicable)		
Normal	Normal	Not applicable	Any	Average of Assessment 1, Assessment 2 and Day 1 (3 tests)
Normal	Abnormal and ≤40% increase from Assessment 1	Not applicable	Any	Average of Assessment 1, Assessment 2 and Day 1 (3 tests)
Normal	Abnormal and >40% increase from Assessment 1	Normal or ≤40% increase from Assessment 1	Any	Average of Assessment 1, Assessment 2, Assessment 3 and Day 1 (4 tests)
		Abnormal and >40% increase from Assessment 1	Not applicable, subject excluded	Not applicable, subject excluded
Abnormal	≤40% increase from Assessment 1	Not applicable	Any	Average of Assessment 1, Assessment 2 and Day 1 (3 tests)

ALT/AST Screening Assessments			Day 1 ALT/AST Assessment	Baseline Value
Assessment 1	Assessment 2	Assessment 3 (if applicable)		
Abnormal	>40% increase from Assessment 1	≤40% increase from Assessment 1	Any	Average of Assessment 1, Assessment 2, Assessment 3 and Day 1 (4 tests)
		>40% increase from Assessment 1	Not applicable, subject excluded	Not applicable, subject excluded

Abbreviations: ALT, alanine aminotransferase; AST, aspartate aminotransferase

New transaminase elevations in subjects with baseline value within the normal range:

For new elevations in transaminases to greater than 2x ULN, repeat measurement should be performed within 48-72 hours¹⁰ of receipt of laboratory results. If elevations persist, subjects should be evaluated for other causes of transaminase elevations and with tests of hepatic function. If no other cause is identified, then the subjects need to be monitored closely (see below), and discontinuation of the IP should be considered.

IP should be discontinued, and the subject followed until resolution of symptoms or signs in the following situations:

- ALT or AST >8x ULN
- ALT or AST >5x ULN for more than 2 weeks
- ALT or AST >3x ULN and (TB¹¹ >2x ULN or INR >1.50¹²)

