- ALT or AST >3x ULN with the appearance of fatigue, nausea, vomiting, right upper quadrant pain or tenderness, fever, rash, jaundice (not attributable to Gilbert's syndrome), and/or eosinophilia (>5.0%)

New transaminase elevations in subjects with baseline ALT or AST > ULN

For new elevations in transaminases to greater than 2x baseline value or total bilirubin >1.5x ULN, repeat measurement should be performed within 48-72 hours¹¹ of receipt of laboratory results. If elevations persist, subjects should be evaluated for other causes of transaminase elevations and with tests of hepatic function. If no other cause is identified, then the subjects need to be monitored closely (see below), and discontinuation of the IP should be considered.

IP should be discontinued, and the subject followed until resolution of symptoms or signs in the following situations:

¹⁰ In cases of isolated AST elevation to the indicated threshold, with a clear non-hepatic source for AST elevation (e.g., evidence of significant concurrent creatine phosphokinase elevation), decision regarding need to proceed with DILI work-up will be based on Investigator judgement.

¹¹ In subjects with Gilbert's syndrome, Direct bilirubin >2 x ULN.

¹² Subjects on anti-coagulation therapy must be assessed individually, as INR criterion will not apply.

Table 3: Discontinuation Criteria in Subjects with Abnormal Baseline ALT or AST Values

Baseline Value of ALT/AST	Criteria to Discontinue IP
<2× upper limit of normal (ULN)	if ALT or AST increases to >5× baseline value
≥2× ULN but <5× ULN	if ALT or AST increases to >3× baseline value
≥5× ULN	if ALT or AST increases to >2× baseline value
Other	
if ALT or AST increase to >2× baseline value AND the increase is accompanied by a concomitant total bilirubin increase to >2× ULN OR the INR concomitantly increases by >0.2.
 
if ALT or AST increase to >2× baseline value in the presence of signs and symptom(s) such as fatigue, nausea, vomiting, right upper quadrant pain or tenderness, fever, rash, jaundice (not attributable to Gilbert's syndrome) and/or eosinophil (>5%)

Abbreviations: ALT, alanine aminotransferase; AST, aspartate aminotransferase; INR, normalized ratio; ULN, upper limit of normal

Close Monitoring for Suspected DILI:

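### SAP Table 6 misstates two of the protocol's laboratory stopping criteria for liver injury; programmed literally, each of those two rows can only over-count

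*SAP*

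**What the plan says.** SAP section 7.10.1 plans a summary of suspected liver injury cases and refers to Table 6 for the criteria. The criteria column is headed "Criteria to discontinue investigational product". Two entries matter here.

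- **Baseline ALT or AST above ULN, combined row.** The SAP prints "ALT or AST >2× baseline value and (BILI >2× ULN or INR >0.2", with the bracket closing after 0.2. Protocol section 7.1.1, Table 3 asks for ALT or AST above twice baseline together with a concomitant rise in total bilirubin to above 2x ULN, "OR the INR concomitantly increases by >0.2".
- **Normal baseline, 5x ULN row.** The SAP prints ALT or AST above 5x ULN and nothing more. The protocol prints "ALT or AST >5x ULN for more than 2 weeks".

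Another row of the same SAP table uses INR as an absolute level: "ALT or AST >3× ULN and (BILI >2× ULN or INR >1.5". That agrees with the protocol's limit of 1.50.

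For abnormal baselines the protocol also sets a lower tier of action: "For new elevations in transaminases to greater than 2x baseline value or total bilirubin >1.5x ULN, repeat measurement should be performed". If the elevation persists and no other cause is found, "then the subjects need to be monitored closely (see below), and discontinuation of the IP should be considered".

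**The concern.** The column heading says that the rows are the criteria for stopping investigational product, so a reader will take each count as the number of subjects who reached a protocol stopping rule. Two rows do not test that rule.

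As printed, the INR term is met by any INR result. The combined row then counts subjects at the protocol's repeat-and-monitor tier as if they had reached the stopping tier. In the 5x ULN row, a single transient value counts as if it had been sustained.

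At stake is the reading of a liver-safety table in a liver-disease trial, where transient elevations could look like stopping criteria that nobody acted on. The same wording probably carries into the final analysis, because SAP sections 7.12.1 and 7.12.3 repeat the Main Study safety summaries on pooled Main and Extension data. No other SAP text restores either missing term.

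**Working it through.** No stated figure needs reproducing, so the check is a row-by-row comparison followed by the logic of the two rows that differ.

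**Step 1. Comparison of SAP Table 6 with protocol section 7.1.1**

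| Baseline | SAP Table 6 | Protocol | Same threshold? |
|---|---|---|---|
| >ULN to <2x ULN | >5x baseline | >5x baseline | yes |
| 2x to <5x ULN | >3x baseline | >3x baseline | yes |
| 5x ULN or more | >2x baseline | >2x baseline | yes |
| >ULN, combined | >2x baseline and (bilirubin >2x ULN or INR >0.2) | >2x baseline with concomitant bilirubin >2x ULN or INR rise >0.2 | **no** |
| Normal | >8x ULN | >8x ULN | yes |
| Normal | >5x ULN | >5x ULN for more than 2 weeks | **no** |
| Normal, combined | >3x ULN and (bilirubin >2x ULN or INR >1.5) | same, with two footnotes | yes |

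Two of seven rows differ. The protocol's two symptom/eosinophilia criteria, one for each baseline group, have no row in Table 6.

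**Step 2. The INR term.** The protocol's own INR levels are 1.30 (exclusion 18e), 1.50 (section 7.1.1) and below 1.7 (best Child-Pugh category, Appendix 8). On that scale an absolute INR above 0.2 is true whenever a result exists. The condition "ALT or AST >2× baseline value and (BILI >2× ULN or INR >0.2" therefore becomes ALT or AST above twice baseline with an INR result available.

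Write b for baseline in multiples of ULN. The printed row starts counting at 2b. Without a bilirubin, INR or symptom finding, the protocol's stopping threshold is 5b for 1<b<2, 3b for 2≤b<5 and 2b for b≥5:

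- b = 1.5: the SAP row counts above 2 × 1.5 = 3.0x ULN; the protocol stops above 5 × 1.5 = 7.5x ULN.
- b = 3: the SAP row counts above 2 × 3 = 6x ULN; the protocol stops above 3 × 3 = 9x ULN.
- b = 5: both are 2 × 5 = 10x ULN. From this baseline upwards the row count is inflated, but every subject in it already meets a stand-alone criterion.

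**Step 3. The duration term.** For a normal baseline the printed row counts any value above 5x ULN. The protocol row needs more than 2 weeks above that level. Values above 5x and up to 8x ULN lasting 2 weeks or less are therefore counted in the SAP row but meet neither the protocol's 5x rule nor its 8x rule. The printed row also contains every case above 8x ULN.

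**Step 4. Direction, by enumeration.** The grid values are assumptions chosen for illustration.

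- Combined row: 4 ALT ratios (1.5, 2.1, 3.5, 5.5) × 3 bilirubin levels (0.8, 1.5, 2.1x ULN) × 4 baseline INRs (0.9 to 1.3) × 5 INR changes (−0.1 to +0.3) = 240 combinations. The SAP row equals ALT above twice baseline alone in 240 of 240. It flags 3 × 2 × 4 × 4 = 96 that the protocol row does not, and misses none.
- 5x ULN row: 4 peaks (4, 5.5, 7, 8.5x ULN) × 5 durations (1, 7, 14, 15, 28 days) = 20 combinations. The SAP row flags 3 × 3 = 9 that the protocol row does not, and misses none. Six of the 9 (peaks 5.5 and 7) are also below the 8x rule.

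The grid treats the laboratory values as simultaneous. Requiring concomitance would only narrow the protocol row, so the direction stands. These counts show direction, not how often such cases would occur.

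**The case against.** **The INR entry is obvious shorthand for a change.** This is the best argument. Since 0.2 is impossible as an absolute cut-off, a programmer who checks the protocol would code a change. That makes the INR over-count conditional on literal programming, and the mock shells that might settle it are in separate documents. It does not make the text right: the same table uses INR 1.5 as an absolute level, SAP section 7.10.2 distinguishes absolute values from increases, and shorthand cannot explain the missing 2 weeks.

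**A duration-free 5x row is a sensible screen.** Main Study visits after Week 4 are 4 to 8 weeks apart, so scheduled data cannot establish a 2-week duration, and a wider net misses nothing. That would be defensible in a table labelled as a screen. This one is headed as stopping criteria.

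**The protocol governs.** It governs subject management, and this stands. Protocol section 9 gives the SAP precedence for analyses, and the summary is an analysis.

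**Stronger readings the documents do not support.** A reader might infer that the whole table, or a total across its rows, over-counts. The SAP specifies no total, and the missing symptom criteria pull the other way: a symptomatic subject with normal baseline, a peak above 3x and up to 5x ULN, and no bilirubin or INR finding meets a protocol criterion but appears in no row. The net sign is unknown. A reader might also infer that subjects would be stopped wrongly, or that the excess would fall unevenly by arm. Stopping follows protocol section 7.1.1, and the documents give no data on liver-enzyme peaks by arm in this trial.

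**Conclusion.** The concern holds for two rows of SAP Table 6. The combined row for baseline above ULN prints an absolute INR where the protocol requires a concomitant increase, and the 5x ULN row omits the 2-week duration. If programmed literally, each row contains every case its protocol counterpart contains and possibly more, so each can only over-count.

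The size cannot be given: the documents hold no case counts, and the excess is zero if no such elevations occur. The other five printed thresholds match. The table is descriptive, and TEAEs leading to discontinuation, laboratory changes and shifts are summarised separately. Subject management and efficacy are unaffected. The correction should be made because it is cheap and the table concerns liver safety; it does not threaten the trial's conclusions.

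**What to change.** In SAP Table 6:

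1. Change the combined row for baseline above ULN to *ALT or AST >2× baseline value with concomitant (BILI >2× ULN or INR increase >0.2)*. State the INR reference and the window that defines concomitant. Baseline is the natural reference, but this is an interpretation, because protocol Table 3 names none.
2. Change the normal-baseline row to *ALT or AST >5× ULN for more than 2 weeks*. Assess it on all post-baseline values including unscheduled repeats, as SAP section 7.10.2 does for vital signs. This must be stated, because SAP section 6.2 otherwise uses unscheduled values only when the scheduled one is missing. List unrepeated single values above 5x ULN separately, so that no signal is lost.
3. Label the table as laboratory criteria only, since the symptom/eosinophilia criteria have no row.
4. Optionally, carry over the protocol's two footnotes to the 3x ULN row: "In subjects with Gilbert's syndrome, Direct bilirubin >2 x ULN", and the INR criterion not applied to anticoagulated subjects, who are assessed individually. Both groups may enrol under exclusion 18.

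The cost is minor wording and programming. INR change from baseline is already planned, because coagulation factors receive change-from-baseline summaries. The limitation is that the 2-week term depends on unscheduled repeat tests. The protocol asks for these within 48 to 72 hours of receiving a result that shows a new elevation, and the separate listing covers cases where none was done.

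### SAP Table 6 writes the abnormal-baseline INR criterion as a level above 0.2 instead of a rise above 0.2, and its normal-baseline rows drop the protocol's two-week duration and two footnotes

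*SAP*

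**What the plan says.** SAP 7.10.1 states: "A summary of suspected liver injury cases according to drug induced liver injury (DILI) criteria will also be presented". The cases are defined in Table 6, where the criteria column is headed "Criteria to discontinue investigational product". Three of its rows differ from the protocol text they appear to restate.

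- **Baseline above ULN.** Table 6 has "ALT or AST >2× baseline value and (BILI >2× ULN or INR >0.2". Protocol 7.1.1, Table 3, row 'Other', requires the same doubling of ALT or AST, with either total bilirubin rising above 2× ULN "OR the INR concomitantly increases by >0.2".
- **Normal baseline, >5× ULN.** Table 6 has "ALT or AST >5× ULN". The protocol's list for normal-baseline subjects has "ALT or AST >5x ULN for more than 2 weeks".
- **Normal baseline, bilirubin/INR.** Table 6 has "ALT or AST >3× ULN and (BILI >2× ULN or INR >1.5". The protocol states the same thresholds but attaches two footnotes. Footnote 11, on bilirubin, reads "In subjects with Gilbert's syndrome, Direct bilirubin >2 x ULN". Footnote 12, on INR, says that anticoagulated subjects are to be judged one by one because the INR criterion does not apply to them. Neither footnote appears with Table 6.

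**The concern.** A table headed as discontinuation criteria should state the protocol's discontinuation criteria. An INR level of 0.2 is no threshold at all, so the '>ULN' row loses its bilirubin/INR condition and becomes a doubling of ALT or AST alone. In the protocol, a doubling alone at abnormal baseline leads to repeat testing, a search for other causes, and consideration of stopping; it is not itself a stopping criterion. Table 6 would therefore report a monitoring trigger as a discontinuation criterion.

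The normal-baseline rows err in the same direction. A single reading above 5× ULN is counted without persistence. An anticoagulated subject whose INR exceeds 1.5 because of treatment is counted automatically once ALT or AST passes 3× ULN. A Gilbert's subject can be counted on unconjugated bilirubin.

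At stake is the accuracy of a planned liver-safety output for a drug given to patients with liver disease. On these rows it would over-count, and the excess cases would have to be explained in the study report.

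**Working it through.** The documents give no figure to reproduce. The check compares the rules term by term and works out what each one counts.

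**Inputs.** SAP Table 6; protocol 7.1.1 and its Table 3; exclusion criterion 18e (INR above 1.30 excluded unless due to anticoagulants). The baseline INR range of 0.8 to 1.3 is assumed, with its upper end anchored on 18e.

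**Step 1: does the INR term discriminate?** Take ALT at 2.1× baseline with normal bilirubin. Cross six baseline INRs (0.8, 0.9, 1.0, 1.1, 1.2, 1.3) with five changes (−0.1, 0, +0.1, +0.2, +0.3), giving 6 × 5 = 30 combinations.

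- As written (INR >0.2): the lowest on-study INR is 0.8 − 0.1 = 0.7, so all 30 of 30 are counted, including those where INR fell.
- Protocol (increase >0.2): only the +0.3 column qualifies, so 6 of 30 are counted.

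These are combinations on a grid, not expected proportions of subjects.

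**Step 2: at what ALT/AST level is a subject counted?** Suppose bilirubin and INR are unchanged and there are no symptoms. With baseline b × ULN, Table 6 as written counts above 2b. Under protocol Table 3 only the band rows apply: above 5b if b < 2, above 3b if 2 ≤ b < 5, and above 2b if b ≥ 5.

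| Baseline (× ULN) | As written (× ULN) | Protocol (× ULN) |
|---|---|---|
| 1.1 | 2 × 1.1 = 2.2 | 5 × 1.1 = 5.5 |
| 1.5 | 2 × 1.5 = 3.0 | 5 × 1.5 = 7.5 |
| 3 | 2 × 3 = 6 | 3 × 3 = 9 |
| 5 | 2 × 5 = 10 | 2 × 5 = 10 |

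The discrepancy affects baselines above ULN and below 5× ULN. At 5× ULN or more, a doubling already qualifies alone.

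**Step 3: normal baseline.** For an isolated single reading with normal bilirubin and INR and no symptoms, the protocol's lowest applicable threshold is 8× ULN, because the 5× ULN rule needs persistence. Table 6 counts the reading above 5× ULN.

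**The case against.** The strongest reply is that 0.2 is an obvious slip. Nobody reads it as an INR level, the text around Table 6 points back to the protocol, and the table shells are separate documents that may already be right. Some of the information is also reported elsewhere: the SAP plans change from baseline for coagulation tests, adverse events leading to discontinuation, and discontinuation reasons. This limits the consequence but does not remove the error. The normal-baseline row of the same table uses INR >1.5, which is a level. Where the SAP means a rise it says so, as in the blood pressure criteria of 7.10.2. Protocol section 9 gives the SAP precedence for analyses.

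A second reply is that Table 6 is a shortened laboratory screen for suspected cases, so dropping the duration is deliberate. The SAP does not say this, and the column heading says otherwise. It is fair, though, that nested thresholds can show severity and that the band rows still capture results on dates without an INR. The rows are not worthless as they stand.

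A reader might also infer that protocol Table 3 is wrong to lack the Gilbert's footnote, since documented Gilbert's subjects may enrol (18c). The documents do not establish that. Table 3 needs a concomitant bilirubin rise as well as a doubling of ALT or AST, so stable Gilbert's hyperbilirubinaemia does not trigger it, and the rule errs towards caution. Relaxing it would be a debatable safety trade-off. A superscript lost in conversion from PDF cannot be excluded either.

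**Conclusion.** The point holds as a minor error in a descriptive safety summary. The '>ULN' row states a wrong INR threshold. Followed literally, it counts abnormal-baseline subjects at ALT/AST levels well below the protocol's: >2.2× against >5.5× ULN at baseline 1.1× ULN, and >6× against >9× ULN at 3× ULN. The normal-baseline rows omit a duration and two footnotes that the protocol attaches to the same criteria. The size rests on a literal reading, an available INR result, unchanged bilirubin and INR, and no symptoms. The number of subjects affected cannot be computed from the documents.

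Three stronger conclusions might be inferred but are not supported.

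- *That dosing decisions or efficacy are affected.* Table 6 feeds a summary only; stopping follows protocol 7.1.1.
- *That correcting these rows would make the summary match protocol stops.* The protocol also stops dosing for ALT/AST >3× ULN (normal baseline) or >2× baseline (abnormal baseline) with symptoms or eosinophilia. Table 6 has no such rows, so some cases would still be missed.
- *That exclusion 18a (250 U/L) leaves almost nobody in the unaffected band of 5× ULN or more.* That limit applies at screening, whereas baseline also averages a Day 1 value on which the baseline table sets no limit.

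**What to change.** In SAP Table 6:

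1. In the '>ULN' row, write the INR term as an increase from baseline >0.2.
2. Restore the protocol's two-week duration to the normal-baseline >5× ULN row, and state how it is derived from the dates of scheduled and repeat results.
3. In the normal-baseline bilirubin/INR row, use direct bilirubin >2× ULN for Gilbert's subjects, and do not apply the INR term to anticoagulated subjects, who are assessed individually.

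Add a note that the table covers laboratory criteria only. Protocol Table 3 needs no change.

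The cost is the wording of three rows and the matching programming. SAP 5.1 already defines the baseline that INR would use. Coagulation tests and direct bilirubin are in the laboratory panel, and medical history and concomitant medications are collected. SAP section 1 allows revision before the database is locked.
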